11.1 Research Ethics Committee (REC) review and reports	
11.2 Peer review	
11.3 Indemnity	
12. DISSEMINATION POLICY	30
13. REFERENCES	31

ii. LIST OF ABBREVIATIONS

BCAA	Branched-chain amino acid
BCKDH	Branched-chain alpha-keto acid dehydrogenase
CI	Chief Investigator
CRF	Case Report Form
CSA	Cross-sectional area
CTIMP	Clinical Trial of Investigational Medicinal Product
GCP	Good Clinical Practice
GLP	Good laboratory practice
MHRA	Medicines and Healthcare products Regulatory Agency
PDC	Pyruvate dehydrogenase complex
PI	Principal Investigator
REC	Research Ethics Committee
SAE	Serious Adverse Event
SOP	Standard Operating Procedure
TMF	Trial Master File

iii. TRIAL SUMMARY

Trial Title	The impact of Acipimox and Salbutamol supplementation on the development of insulin resistance and anabolic resistance during forearm immobilization in healthy, young volunteers	
Short title	Forearm immobilization, metabolic health, and muscle loss	
Trial Design	Randomized, double-blind, placebo-controlled trial with three parallel groups	
Study category	Basic science study involving procedures with human participants	
Trial Participants	Young healthy recreationally active males and females	
Planned Sample Size	45	
Treatment duration	2 days of forearm immobilization plus drug or placebo ingestion	
Planned Trial Period	Minimally 12 days (screening, baseline metabolic test day, approximate 7 days waiting period, 2 days forearm immobilization), maximally 33 days (waiting period can be up to 4 weeks, depending on availability of the participant).	
Study sites	
Royal Devon & Exeter NHS Foundation Trust Clinical Research Facility (CRF) and Clinical Trials Pharmacy Activities: screening and consenting (CRF), forearm cast application and removal (CRF), metabolic testing (CRF), drug dispensing to study participants (Pharmacy)
 
Nutritional Physiology research laboratories St Luke's Campus, University of Exeter Activities: preparation of a standardised diet, plasma analyses. If required: screening and consenting, forearm cast application
	
	Objectives	Outcome Measures
Primary	Determine the impact of reduced muscle lipid availability and increased glycolytic flux on forearm glucose uptake during short-term forearm immobilization in healthy volunteers	Forearm glucose uptake

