Secondary	Determine the impact of reduced muscle lipid availability and increased glycolytic flux on muscle protein synthesis, and forearm nutrient balance during short-term forearm immobilization in healthy volunteers	Postabsorptive and postprandial muscle protein synthesis Forearm branched-chain amino acid and fatty acid balance Forearm volume
Medication to be administered	Administered during the 2-day forearm immobilization period: Acipimox OR Salbutamol OR Placebo	
Formulation, Dose, Route of Administration	Acipimox, 250 mg, 4 times daily, oral administration Salbutamol, 4 mg, 4 times daily, oral administration	

	Placebo, no active ingredients, 4 times daily, oral administration
CTIMP? (yes/no)	No (confirmation from MHRA is included in this application)

iv. FUNDING AND SUPPORT IN KIND

FUNDER(S)	FINANCIAL AND NON FINANCIAL SUPPORT GIVEN
Wellcome Trust [name]	Sir Henry Wellcome Postdoctoral Fellowship to [name]
Sport and Health Sciences College of Life and Environmental Sciences University of Exeter [name]	

v. ROLE OF TRIAL SPONSOR AND FUNDER

This study is funded by a 4-year Sir Henry Wellcome Postdoctoral Fellowship to [name]. [name] and [name] were responsible for the study design. The University of Exeter acts as a sponsor for this study. [name] will be responsible for data collection and analysis, decision to publish, and preparation of manuscript(s).

The UK Policy Framework for Health & Social Care and Medicines for Human Use (Clinical Trials) Regulations and Amendment Regulations 2006 require that all health-related research has a sponsor and sets out the responsibilities of the sponsor. The sponsor takes overall responsibility for the initiation, management and financing (or arranging the financing) of the research and must satisfy itself that appropriate arrangements are in place for management, monitoring and reporting of research activity. It is recognised that the sponsor can delegate specific responsibilities to any other individual or organisation that is willing and able to accept them. However, any delegation of responsibilities to another party should be formally agreed and documented by the sponsor.

vii. Protocol contributors

[name] – protocol development and scientific critique

[name] – protocol development and scientific critique

[name] (medical collaborator) – protocol development and risk assessment

[name] – Lead statistician

[figure not shown]

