4 OBJECTIVES AND OUTCOME MEASURES/ENDPOINTS

4.1 Primary objective

Determine the impact of reduced muscle lipid availability and increased glycolytic flux on forearm glucose uptake during short-term forearm immobilization in healthy volunteers.

Research question: Does lowering muscle lipid availability and increasing glycolytic flux attenuate the immobilization-induced decline in forearm glucose uptake?

Null hypothesis: Lowering muscle lipid availability and increasing glycolytic flux does not attenuate the immobilization-induced decline in forearm glucose uptake.

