- At t = 2.5 h, a hyperinsulinaemic-euglycaemic-hyperaminoacidaemic clamp will be started. For this, insulin will be infused at a rate of 50 mU·m⁻²·min⁻¹, and a simultaneous infusion of 20% glucose will be started to maintain euglycaemia at 5.0 mmol·L⁻¹. A 0.3% potassium chloride solution will be infused in the (to be) immobilized arm at a rate of 1 ml/kg body weight/h during the 3-h clamp to maintain plasma potassium concentrations [25]. Hyperaminoacidaemia will be induced by infusion of an amino acid solution (Primene 10%, Baxter) at BCAA concentrations of 700 μmol·L⁻¹. This concentration was chosen as it is the average postprandial BCAA concentration following mixed meal ingestion in the pilot study. Primene will be 7% enriched with L-[ring-²H₅]-phenylalanine to prevent a decrease in plasma enrichments with Primene infusion. Measurements of blood glucose (Yellow Springs Instruments; every 5 min) and BCAA (spectrophotometric assay, [26]; every 20 min) concentrations will be performed at the bedside, and the infusion rate of glucose and amino acids adjusted accordingly to maintain steady state. Throughout the entire 5.5 h infusion period, repeated arterialised-venous (AV) and deep-venous (V) blood samples will be taken in order to calculate forearm AV-V balance of glucose (i.e. insulin sensitivity), amino acids, and free fatty acids using the Fick principle [27]. Prior to every blood sample, brachial artery blood flow will be measured using Doppler ultrasound.

- After 2 hours of the 3h clamp, a single dose of 10 mg metoclopramide hydrochloride will be administered intravenously in an antecubital elbow cannula, to prevent potential gastrointestinal issues during the final hour of the clamp.
- Following the 3 h clamp, infusion of insulin, amino acids and stable isotope amino acids will be stopped while infusion of glucose will be decreased in a stepwise manner based on blood glucose concentrations. The last 30 min of the clamp will be used to calculate the mean glucose infusion rate (GIR) and mean amino acid infusion rate. Participants will be monitored for minimally 20 min following cessation of the glucose infusion before they are allowed to leave the laboratory.

Forearm casting and drug dispensing (visit 3; to take place between 7 and 28 days after visit 2):

- In the morning at 7:30 AM, participants will visit the Clinical Research Facility at the Royal Devon & Exeter NHS Foundation Trust in an overnight fasted state.

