- A fiberglass forearm cast (randomized between dominant and non-dominant arm) will be applied from below the elbow to approximately 2-3 cm below the finger tips, to immobilize the wrist. Participants will be given a sling to wear at all times, except for during sleeping and showering. A waterproof cover will be provided to cover the cast during showering.
- Participants will then receive the food products for the controlled diet, which they will consume during the 2 days of forearm immobilization. Participants will be fed in energy balance, with energy requirements calculated as basal metabolic rate (Henry equations) times an activity factor (IPAQ questionnaire). The diet consists of 1.2 g/kg body weight/day protein (approx. 10-15 en%), 50-55 en% carbohydrate, and 35 en% fat. The diet will be composed of three main meals (i.e. breakfast, lunch, dinner) and snacks, and will contain normal food products. A food diary including recipes for the evening meals will be given, and the entire diet will be explained.
- Lastly, participants will visit the Clinical Trials Pharmacy at RD&E to collect their allocated treatment. Instructions on the times and way to ingest the treatment is provided by trained staff, and a treatment log will be provided. The first out of eight doses will be taken.
- Participants will be sent home, and will return to the CRF two days later for visit 4.

Post-immobilization metabolic test day (visit 4):

- In the morning at 8 AM, participants will visit the Clinical Research Facility at the Royal Devon & Exeter NHS Foundation Trust in an overnight fasted state.
- The metabolic test day will be repeated.
- The fiberglass cast will be removed.

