7 TRIAL TREATMENTS

The present study is a basic physiology study, which aims to elucidate mechanisms underlying muscle atrophy by studying muscle metabolism in conditions of pharmacologically altered substrate availability. Participants will be randomized to receive one of two drugs (Acipimox and Salbutamol) or a placebo, to be taken orally during the 2-day forearm immobilization period. Products will be prescribed by [name], after thorough checking for the listed in- and exclusion criteria (Section 6).

All products will be taken 4 times daily, with or after the three main meals (i.e. breakfast, lunch, dinner), and before bed.

Participants will be able to contact the CI 24/7, and [name] will be available for advice throughout the supplementation period.

The study products are described below:

Acipimox

The drug Acipimox is a nicotinic acid analogue that inhibits adipose tissue lipolysis, lowers intramuscular lipid metabolites, and improves insulin sensitivity. Acipimox will be given in 250 mg capsules, taken 4 times daily, as this dose has been shown to improve insulin sensitivity in type 2 diabetes patients within a few days [20].

Acipimox may cause some mild-moderate side effects in approximately 2 out-of 10 people. These side effects can include: skin rash; red 'flushed' skin; itching; sensations of hot skin. Less common effects include stomach pain and weakness.

Salbutamol

The drug Salbutamol is a β 2-adrenoceptor agonist commonly used as a bronchodilator in asthma. In addition, β 2-agonists have been shown to stimulate glycogenolysis and glycolytic flux [21], and exert a hypertrophic effect [22] by increasing muscle protein synthesis and decreasing proteolysis [23, 24]. Salbutamol will be given in 4 mg tablets, taken 4 times daily, as this dose has been shown to lead to a significant increase in lean mass in [22].

Salbutamol may cause mild-moderate side effects in approximately 1 out-of 10 people. These side effects can include fine tremor ('shaking', especially of the hands), headache, dizziness, and nausea. Less common side effects include arrhythmias, low blood pressure, and muscle pain.

Placebo

The placebo supplement will contain lactose, microcrystalline cellulose, pregelatinised starch, sodium starch glycolate, and magnesium stearate. These are inert substances widely used in many pill and tablet formulations, and are unlikely to cause toxicity when taken orally.

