9.3.2 Primary outcome analysis

The primary outcome measure for this study is forearm glucose uptake, measured during the steady-state phase of a 3-h hyperinsulinaemic-euglycaemic-hyperaminoacidaemic clamp. A two-way ANOVA, with and treatment (placebo vs Acipimox vs Salbutamol) as between-subjects factor and time (pre vs post immobilization) as within-subjects factor. A Bonferroni post-hoc test will be used to locate individual differences.

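### Every arm is cast and drug is given only with the cast, so the primary test cannot separate a general rise in glucose uptake from protection against disuse, and GIR, which bears on this, is calculated but not analysed

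*Combined protocol and SAP*

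**What the plan says.** The Trial Summary describes a "Randomized, double-blind, placebo-controlled trial with three parallel groups" and gives the medication as "Administered during the 2-day forearm immobilization period: Acipimox OR Salbutamol OR Placebo". Under section 5.5 the baseline clamp (visit 2) takes place before casting and before any drug. At visit 3 the cast is applied, the treatment is collected, and "The first out of eight doses will be taken". Visit 4 repeats the clamp after two days of cast and treatment. No group takes a drug without a cast, and deep-venous blood is drawn from one arm only.

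The research question in section 4.1 is "Does lowering muscle lipid availability and increasing glycolytic flux attenuate the immobilization-induced decline in forearm glucose uptake". Section 9.3.2 analyses forearm glucose uptake by ANOVA, with treatment as the between-subjects factor and "time (pre vs post immobilization) as within-subjects factor".

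For Acipimox, section 7 justifies the dose "as this dose has been shown to improve insulin sensitivity in type 2 diabetes patients within a few days".

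On whole-body glucose disposal, section 5.5 says "The last 30 min of the clamp will be used to calculate the mean glucose infusion rate (GIR". GIR does not appear among the primary or secondary outcomes (sections 4.3 to 4.5 in the contents list, numbered 3.3 to 3.5 in the body), in the baseline data (9.3.1), or in the analyses (9.3.2 and 9.3.3).

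**The concern.** The pre-to-post change in a drug group combines the effect of the cast, any effect of the drug on glucose uptake in muscle generally, and any effect of the drug that depends on the muscle being immobilised. Subtracting the placebo change removes the first component and leaves the sum of the other two.

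The section 4.1 question concerns the last component. A drug that raises glucose uptake equally in every muscle, cast or not, would offset the decline numerically without acting on the process that causes it. In a study whose stated purpose is to elucidate mechanisms (section 7), this difference matters to the conclusion. A positive primary result could be published as attenuation of disuse-induced insulin resistance when the data show only higher uptake on drug than on placebo.

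GIR bears on the question because the cast covers only the area from below the elbow to near the fingertips. Whole-body glucose disposal therefore comes mostly from tissue that was not immobilised. If GIR is not named in advance, any later use of it will be post hoc.

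**Working it through.** **1. The plan's own figures (section 9.1).** Inputs: placebo change -13% (SD 8), Acipimox 0% (SD 8), Salbutamol -4.3% (SD 6), alpha 0.05, power 80%. Method: two-sample t-test, noncentral t, two-sided.

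- Acipimox: d = 13/8 = 1.625, giving n = 8 per group (power 85.6%).
- Salbutamol: d = 8.7/√((64 + 36)/2) = 8.7/7.07 = 1.23, giving n = 12 per group (power 82.1%).
- Recruitment: 12/(1 - 0.20) = 15 per group, and 3 × 15 = 45.

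All stated sample sizes are reproduced.

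**2. General effect that would reproduce the planned results with no protection against disuse.** Set uptake at visit 2 to 1. After the cast alone it is 1 - 0.13 = 0.87. If the drug multiplies uptake in any muscle by (1 + r), visit 4 uptake is 0.87 × (1 + r).

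- Acipimox, planned 0% change: 1 + r = 1/0.87 = 1.149, so r = 14.9%. Check: 0.87 × 1.149 = 1.00.
- Salbutamol, planned -4.3% change: 1 + r = 0.957/0.87 = 1.10, so r = 10.0%. Check: 0.87 × 1.10 = 0.957.

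In points of baseline uptake these rises are 13 and 8.7.

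**3. What the primary test would then show.** Suppose the drug adds g points in any forearm and gives no specific protection. The expected drug-group change is -13 + g, the same as for a specific rescue of g points. With 12 completers per group and SD 8, the drug-placebo contrast is significant with these probabilities:

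| g (points) | alpha 0.05 | alpha 0.05/3 |
|---|---|---|
| 8.7 | 72% | 54% |
| 13 | 97% | 91% |

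The 0.05/3 column assumes that the Bonferroni step covers three pairwise comparisons. In simulation with g = 13 for Acipimox and 0 for Salbutamol (SD 8 in every group), the overall treatment-by-time test rejected in 98% of trials. The test has good power for the total effect and carries no information on how it divides.

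**4. What GIR could add.** The documents give no SD for the change in GIR, so a range is assumed (12 per group, two-sided 0.05):

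| Assumed SD of GIR change (points) | Power for a 13-point difference | Difference detectable with 80% power |
|---|---|---|
| 8 | 97% | 9.6 |
| 10 | 86% | 12 |
| 15 | 53% | 18 |
| 20 | 33% | 24 |
| 25 | 23% | 30 |

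A clear drug-placebo difference in GIR change would point to a general effect. A non-significant one says little if the SD is about 15 points or more, so the confidence interval should be reported and not only the test.

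**5. Which forearm is sampled.** Section 5.5 places the deep-venous cannula in the non-immobilised arm at visit 2 and says the test day is repeated at visit 4. Read literally, the primary outcome comes from the uncast forearm, contrary to section 4.1. Steps 2 and 3 assume the cast forearm is sampled. On the literal reading, setting the forearm effect beside GIR would compare uncast muscle with the whole body.

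**The case against.** The strongest reply is that the stated objective is met. The Trial Summary and section 4.1 ask for the impact of altered substrate availability on forearm glucose uptake during short-term immobilisation, and randomised drug versus placebo under a cast estimates that without bias. This stands. The difficulty is confined to the attenuation wording of the research question and null hypothesis in 4.1, and to the matching rationale in 9.1. A reader might infer that the primary analysis is invalid; the documents do not support that.

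A reader might also infer that a general effect is expected. The documents do not go so far. Section 7 reports such an effect only for Acipimox and only in patients with type 2 diabetes, whereas section 6.2 excludes diagnosed metabolic impairment. For Salbutamol no comparable evidence in people is described. By the schedule in sections 5.5 and 7, the eighth dose falls before bed on the evening before visit 4, so how much of any general effect persists into the clamp is unknown. The 14.9% and 10.0% are solved from the planning targets and are not estimates.

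The controlled diet, "which they will consume during the 2 days of forearm immobilization", might be read as a further confounder. It is common to all arms and cancels in the drug-placebo contrast. It affects only the reading of the time effect as immobilisation alone.

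Finally, nothing in the protocol says that GIR is collected to separate the two effects; that use is proposed here. GIR is a whole-body measure, and no glucose tracer is described that would remove changes in hepatic output. This stands, and it limits GIR to a supporting role.

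**Conclusion.** The point holds as one of interpretation and reporting. The treatment-by-time test validly estimates the total drug effect on forearm glucose uptake during immobilisation. It cannot divide that effect into general sensitisation and specific protection, because drug and cast always occur together and one forearm is sampled. Under the plan's own 13% decline, general rises of 14.9% and 10.0% are sufficient to reproduce the two planned results with no protection against disuse. This rests on the planning values in section 9.1, on a general effect that acts equally on cast and uncast muscle, and on sampling in the cast forearm, which section 5.5 as written contradicts.

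It may be tempting to let a forearm-to-GIR ratio decide whether attenuation may be claimed. The documents do not support such a rule. They give no SD for GIR or for the ratio and no criterion for one effect exceeding the other, and they describe nothing to separate hepatic output. A supportive measure should not decide the main conclusion.

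**What to change.** 1. Reconcile section 5.5 (deep-venous cannula in the non-immobilised arm, repeated at visit 4) with the objective in section 4.1. The comparison below can be interpreted only if the cast forearm is the one sampled.
2. Name mean GIR over the last 30 minutes of the clamp, at visits 2 and 4, as a secondary outcome in section 4.4 (3.4 in the body) and in 9.3.3. Analyse it with the same model as the primary outcome, and report each drug-minus-placebo difference in change with its confidence interval beside the forearm effect.
3. Word the primary conclusion as the drug's effect on forearm glucose uptake during immobilisation compared with placebo. Present specific attenuation of disuse-induced resistance as an interpretation informed by GIR, with no ratio-based gate.
4. State in advance that a null GIR result will not be read as absence of a general effect, because GIR is imprecise at this sample size and includes hepatic effects.

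Items 2 to 4 need a few sentences of protocol and SAP text and one extra model on data already collected, with no added participants, visits or samples and no change to the sample size. A direct test would need both forearms sampled or a drug-without-cast comparison; that is a change of design and is not required for the objective as stated.

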2 RATIONALE

We hypothesize that muscle disuse alters intramuscular glucose and fatty acid metabolism, and their interaction, which consequently leads to decreases in insulin sensitivity and anabolic sensitivity. The primary aim of this study is therefore to determine the impact of reduced muscle lipid availability and increased glycolytic flux on forearm glucose uptake during short-term forearm immobilization in healthy volunteers. A secondary aim is to assess whether these simple pharmacological interventions have an impact on muscle mass loss during the first few days of immobilization; a critical period in a range of clinical scenarios, but one where we still do not know the mechanisms underpinning muscle loss.

We will perform a randomized, double-blind, placebo-controlled study in healthy, young volunteers that will directly characterise the metabolic status of inactive muscle tissue in situations of altered substrate availability. In order to unravel the underlying mechanisms and capture metabolic changes, it is crucial to study the muscle immediately after the onset of insulin resistance. Therefore, participants will undergo 2 days of forearm cast immobilisation, combined with fully-controlled nutritional intake. Prior to and immediately following immobilisation, a metabolic test day will be performed using the AV-V forearm balance technique combined with stable isotope amino acid infusion to quantify muscle glucose uptake (i.e. insulin sensitivity, the primary outcome measure), muscle protein synthesis and breakdown, as well as fatty acid and BCAA balance in the postabsorptive state and during a 3h hyperinsulinaemic-euglycaemic-hyperaminoacidaemic clamp. This clamp will be used as the hyperinsulinaemic-euglycaemic clamp (golden standard for measuring insulin sensitivity) is associated with hypoaminoacidaemia [18], which likely impacts on muscle protein synthesis [19]. By clamping glucose and amino acid concentrations, glucose uptake and muscle protein synthesis can be quantified under steady-state conditions while insulin concentrations are controlled for.

The following interventions will be used to alter muscle substrate availability in a randomised, double-blind, placebo-controlled study with a parallel-group design:

1. Placebo
2. Acipimox, an anti-lipolytic agent which decreases circulating lipids, inhibits intramuscular lipid accumulation and thereby reduces lipid supply to the mitochondria [20].

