3.5 Table of endpoints/outcomes

Objectives	Outcome Measures	Timepoint(s) of evaluation of this outcome measure (if applicable)
Primary Objective Determine the impact of reduced muscle lipid availability and increased glycolytic flux on forearm glucose uptake during short-term forearm immobilization in healthy volunteers.	Forearm glucose uptake	During the steady-state phase of the hyperinsulinaemic-euglycaemic clamp, during the metabolic test days prior to and immediately following 2 days forearm immobilization
Secondary Objectives Determine the impact of reduced muscle lipid availability and increased glycolytic flux on muscle protein synthesis, and forearm nutrient balance during short-term forearm immobilization in healthy volunteers	Postabsorptive and postprandial muscle protein synthesis Forearm branched-chain amino acid and fatty acid balance Forearm volume	During the metabolic test days

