5.5 Trial procedures

Please refer to page 11 for trial flow chart and schematic of the metabolic test days. The trial procedures are described below:

Screening visit (visit 1):

- Firstly, participants will be asked to meet the investigator so that the study can be explained to them in detail, and it is clear what they can expect from the research team and what will be expected of them. Assuming they are happy with what has been discussed, they will then provide written consent. Subsequently, they will complete a medical screening questionnaire and have their height, weight, body composition (Bodpod), and blood pressure measured.
- Participant's caloric requirements will be calculated by estimating Resting Metabolic Rate via the Henry equation, and then multiplying this value by an activity factor derived from the International Physical Activity Questionnaire (IPAQ) questionnaire.
- Forearm volume will be measured via anthropometry.
- Participants will be asked for any allergies or intolerances to ensure they can eat everything they will receive as part of the standardized diet.
- Participants will be provided with a food diary to record their habitual dietary intake for 3 consecutive days, including 2 week days and 1 weekend day.

Baseline metabolic test day (visit 2):

- Approximately 1 week prior to casting, at 8 AM, participants will visit the Clinical Research Facility at the Royal Devon & Exeter NHS Foundation Trust in an overnight fasted state for a metabolic test day.
- The following cannulas will be inserted by a trained research nurse: 1) retrogradely into a deep antecubital vein (draining the muscle bed) of the non-immobilised arm, 2) retrogradely into a superficial dorsal hand vein of the to-be-immobilised hand, and 3) anterogradely into an antecubital vein in the elbow of the to-be-immobilised arm for infusion of insulin, glucose, amino acids, and stable isotope amino acids. The cannulated hand will be placed into a hand-warming unit (air temperature 55°C) to arterialize the venous drainage of the hand.
- After insertion of all cannulas, a primed, continuous stable isotope infusion of L-[ring-²H₅]-phenylalanine (prime: 0.5 mg·kg⁻¹, infusion 0.5 mg·kg⁻¹·h⁻¹) will be started with participants in a supine position. Using this tracer approach we will be able to calculate muscle protein synthesis and plasma leucine oxidation.

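### As described in section 5.5, arterialised hand sampling for the primary outcome cannot be repeated at visit 4, because the hand to be cannulated and warmed lies under the cast; all cannula sites and the time of cast removal need to be stated together

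*Combined protocol and SAP*

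**What the plan says.** Section 5.5 assigns three cannulas at the baseline test day (visit 2):

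- deep-venous sampling: "retrogradely into a deep antecubital vein (draining the muscle bed) of the non-immobilised arm";
- arterialised sampling: "retrogradely into a superficial dorsal hand vein of the to-be-immobilised hand", after which "The cannulated hand will be placed into a hand-warming unit";
- infusion: an elbow vein on the side to be cast. The potassium chloride instruction, worded to cover both test days, agrees: it "will be infused in the (to be) immobilized arm".

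At visit 3 the cast "will be applied from below the elbow to approximately 2-3 cm below the finger tips, to immobilize the wrist".

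Visit 4 has three bullets: arrive fasted at 8 AM; repeat the metabolic test day; and, last, "The fiberglass cast will be removed". No change of arm or cannula site is given. Section 3 counts three cannulas on each test day, one of them in the hand, so a hand line is needed at visit 4 too.

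On timing, section 2 says "Prior to and immediately following immobilisation, a metabolic test day will be performed", and the endpoint table (section 3.5) has the primary outcome measured "during the metabolic test days prior to and immediately following 2 days forearm immobilization".

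**The concern.** The arterialised sample is one half of the arteriovenous difference that defines the primary outcome. If its site cannot be reached at the second test day, the post-immobilisation value cannot be obtained by the method described. Site staff would have to take the cast off or open it early, or use the other hand at visit 4 only. The protocol authorises none of these, and each makes the second measurement differ from the first in a way unrelated to treatment. The outcome is a within-person change, and the design counts on 12 completers per group, so a mismatch between the two set-ups matters.

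**Working it through.** The main check is a cross-reading; section 9.1 contains no figure for this point.

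**1. Is the hand under the cast?** The hand line and the warming unit are assigned to the side to be cast. The cast starts below the elbow and ends 2-3 cm short of the finger tips. The back of the hand is therefore covered. The elbow vein used for infusion is above the cast and stays accessible.

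**2. Is the cast on during the visit 4 test?** The bullets for visit 4 carry no explicit word of sequence. Those for visits 2 and 3 run in time order, and read in the same way, removal comes after the test day. Nothing in the text says otherwise.

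**3. Do sections 2 and 3.5 settle it?** Casting is at the 7:30 AM visit and the second test starts at 8 AM two days later: 48 h + 0.5 h = about 48.5 h. A test beginning then follows two days of immobilisation whether the cast is on or off. These sections do not decide the order.

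**4. What happens if the arm labels change?**

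| Reading | Warmed hand at visit 4, cast on | Forearm described by the balance |
|---|---|---|
| As written | under the cast | never cast |
| Two sampling labels interchanged | free | the cast forearm, with infusion in the same arm unless it is moved too |
| Hand line alone moved | free, but on the deep-venous side | never cast, with the hand heated on the sampled side |

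As written, the plan has two faults: the hand line is inaccessible, and the balance describes a forearm that is not immobilised, contrary to the primary objective. Interchanging the sampling labels removes both and makes the listed order workable. The infusion side is stated twice, in the cannula list and in the potassium instruction, so it has to be settled in the same edit.

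**5. What could a changed set-up do to the comparison?** Section 9.1 uses a change of -13±8% on placebo and 0±8% on acipimox. The plan's effect size is reproduced: 13/8 = 1.625. For salbutamol (-4.3±6%) the difference is 13 - 4.3 = 8.7, the pooled SD is √((64+36)/2) = 7.07, and 8.7/7.07 = 1.23, also as stated.

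- Suppose visit 4 practice adds the same shift b (percentage points) in every group. The placebo change becomes -13 + b, but the acipimox contrast is (0 + b) - (-13 + b) = 13. The pre-post change moves; the group contrast does not.
- Suppose practice varies between participants with SD s, independent of the true change. The effect sizes become 13/√(64 + s²) and 8.7/√(50 + s²). Both fall as s rises. The documents give no value for s or b, so the loss cannot be calculated.

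**The case against.** Several counter-arguments are fair.

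- **The order is inferred.** Section 5.5 refers to a flow chart and a schematic of the test days, which were not available for this review. They may show cannula sites and cast timing, and staff may not in fact be left to improvise. This stands as a limit on the point. It does not reconcile the written procedure; if the figures do give the answer, the text should match them.
- **The cause may be a labelling slip.** This is plausible and would explain the conflict, but the current text still has to be corrected.
- **A common shift largely cancels.** This stands. The powered comparisons are drug versus placebo on the change, so a set-up difference shared by three randomised groups mainly affects the overall time effect.

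A reader might also draw stronger conclusions that the documents do not support.

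- That the order decides whether the sampled forearm is still cast or has been free for hours at the primary measurement. On the literal text the sampled forearm is never cast, so this needs the labels corrected first. It also takes the last 30 min of the clamp as the primary window. Section 5.5 gives that window only for the mean glucose and amino acid infusion rates; for forearm uptake, sections 3.5 and 9.3.2 say only steady state.
- That sections 2 and 3.5 require the cast to come off before the test. Their wording fits either order.
- That poorer arterialisation at visit 4 would imitate a decline relevant to the treatment effect. A shared artefact would not do that, and nothing suggests that practice would differ by treatment group.

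**Conclusion.** The inconsistency is real. With the hand line and warming on the side to be cast, a cast covering that hand, and removal listed after the repeated test day, the arterialised samples for the primary outcome cannot be taken at visit 4 from the stated site. This is more than missing detail, because the written steps are incompatible with one another.

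The conclusion rests on two assumptions: that the visit 4 bullets are in time order, and that the missing figures do not override them. If removal before cannulation is intended, the text is out of sequence and the interval from removal to clamp is unspecified, so an edit is needed on either reading.

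The effect on glucose uptake cannot be sized from the documents. A uniform departure would mainly bias the pre-post change; an inconsistent one would reduce precision for the group comparison. The problem cannot be separated from the assignment of the deep-venous line to the arm that is not immobilised, which is arguably the larger fault, and the two should be corrected together.

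**What to change.** Reconcile sections 2, 3.5 and 5.5 in a single edit.

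1. For both test days, state which arm carries the deep-venous, the arterialised hand and the infusion cannulas, and bring the potassium chloride instruction into line. The deep-venous line should drain the immobilised forearm named in the primary objective. The warmed hand should be accessible, and the same hand, at both visits. Name the arm for the Doppler flow measurement as well, since section 5.5 does not.
2. State when the cast is removed relative to cannulation and the clamp, identically for every participant.
3. Check the flow chart and the test-day schematic against the revised text.

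The hand line should not be moved on its own: both sampling lines would then lie in the arm that is never cast, with the hand heated on the sampled side.

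The cost is protocol wording and a site instruction. No extra visits, samples or participants are needed.
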